2.3.2. Benefit Assessment

PF-07321332/ritonavir will not provide any clinical benefit to healthy participants in this study. Any anticipated benefit to participants would be in terms of contribution to the process of developing a new therapy in an area of unmet medical need.

2.3.3. Overall Benefit/Risk Conclusion

PF-07321332/ritonavir are not expected to provide any clinical benefit to healthy participants in this study. Taking into account the measures taken to minimize risk to participants of this study, the potential risks identified in association with administration of PF-07321332/ritonavir are justified by the anticipated benefit, in terms of contribution to the process of developing a new therapy in an area of unmet medical need.

3. OBJECTIVES AND ENDPOINTS

Objectives	Endpoints
Primary:	Primary:

To characterize the plasma PK of PF-07321332 when PF-07321332/ritonavir is administered in healthy Chinese participants	
PF-07321332 plasma PK parameters:
Day 1: C_{max}, T_{max}, AUC_{12}Day 5, 8,10 (pre-dose and 12 hours after last dose): C_{trough}Day 10: C_{max}, T_{max}, AUC_{tau}; and if data permit, AUC_{last}, C_{av}, R_{ac}, $R_{ac,Cmax}$, PTR, CL/F, V_z/F and $t_{1/2}$
Secondary:	Secondary:

To determine the safety and tolerability of PF-07321332/ritonavir in healthy Chinese participants after dose administrationTo characterize the plasma PK of ritonavir following PF-07321332/ritonavir administration in healthy Chinese participants	
AEs, clinical safety laboratory tests, vital signs, 12-lead ECGsRitonavir plasma PK parameters:
Day 1: C_{max}, T_{max}, AUC_{12}Day 5, 8,10 (pre-dose and 12 hours after last dose): C_{trough}Day 10: C_{max}, T_{max}, AUC_{tau}; and if data permit, AUC_{last}, C_{av}, CL/F, V_z/F and $t_{1/2}$
CCI	

4. STUDY DESIGN

4.1. Overall Design

This is a Phase 1, open-label study to estimate the PK, safety and tolerability of PF-07321332 when PF-07321332/ritonavir is administered in healthy Chinese participants. The study will

consist of 1 treatment: 10-day oral doses of 300 mg PF-07321332/100 mg ritonavir. A total of approximately 14 healthy male and/or female participants will be enrolled into the study to ensure at least 12 participants will complete the study. Participants who discontinue from the study for non-safety reasons may be replaced at the sponsor's discretion in collaboration with the Investigator.

The total duration of participation in this study is approximately 73 days, including a screening period of up to 28 days to confirm eligibility, treatment duration about 12 days (10 days of dose duration and another 2 days of full PK profile duration) and a follow-up period of approximately 28-35 days post the last dose of study intervention.

Participants will be admitted to the CRU on Day -1 and may be discharged at the discretion of the investigator following completion of assessments per protocol requirement on Day 12 (2 days after last dose on Day 10).

All of participants will receive PF-07321332 and ritonavir together. The dose regimen is PF-07321332/ritonavir 300/100 mg q12h for a total of 19 oral doses (Day 1 to Day 10). The first dose and the last dose will be recommended to be administrated on Day 1 and Day 10 morning, respectively, for intensive PK sample collection feasibility. The evening dose will not be given on Day 10.

Following discharge on Day 12 after last PK and safety assessment, follow-up contact may occur via telephone and must occur 28 to 35 days after the last dose of investigational product, or via on-site visit if it is necessary per investigator's evaluation. Participants who prematurely discontinue for non-safety related reasons may be replaced, at the discretion of the principal investigator and sponsor study team.

4.2. Scientific Rationale for Study Design

CCI Considering the dose duration in Phase 2/3 studies may be up to 5 or 10 days, a 10-day safety profile in Chinese healthy participants would be beneficial to describe the safety characteristic in the Chinese population and justify the ethnic difference. Therefore a 10-day dosing duration is planned, based on maximum duration of dosing in global C4671006 study.

The purpose of the study is to investigate the PK, safety and tolerability of PF-07321332 following repeated oral doses in combination with a PK boosting agent ritonavir in Chinese healthy adults. One (or more) suitable Western study(ies) will be selected for comparison between Western and Chinese populations. This may involve comparison of Day 1 data and/or steady-state data (generally reached by Day 2) with the data obtained from the Chinese Phase 1 study. **CCI**

4.2.1. Choice of Contraception/Barrier Requirements

[figure not shown]
Human reproductive safety data are limited for PF-07321332, but there is no suspicion of human teratogenicity based on the intended pharmacology of the compound. Therefore, the use of a highly effective method of contraception is required (see [Appendix 4](#)).

4.3. Justification for Dose

This study is designed to estimate the PK, safety of multiple dose administration of PF-07321332 and ritonavir when both of them administered together. A dose of 300 mg PF-07321332, pharmacokinetically enhanced with 100 mg ritonavir, to be administered q12h for 10 days will be used in this study. This dose is the intended therapeutic dose to be evaluated in Phase 2/3 studies and is appropriate considering concomitant administration of PF-07321332 with ritonavir provides near maximal CYP3A4 inhibition.

When co-administered with ritonavir, doses of PF-07321332 up to 750 mg single dose and 500 mg q12h for 10 days were generally safe and well tolerated based on preliminary data from the Phase 1 Study C4671001. There have been no deaths or SAEs or SUSARs reported. Based on review of preliminary (unaudited) data, all reported adverse events have been of mild intensity. There were no clinically meaningful findings in vital signs, ECG, or potential Hy's Law cases reported during the study.

Furthermore, doses up to 500 mg PF-07321332/100 mg ritonavir administered orally q12h for 10 days have been studied in healthy participants in Study C4671001. **CCI**

4.4. End of Study Definition

The end of the study is defined as the date of the last scheduled procedure shown in the **SoA** for the last participant in the trial.

A participant is considered to have completed the study if he/she has completed all periods of the study, including the last scheduled procedure shown in the [SoA](#).

5. STUDY POPULATION

This study can fulfill its objectives only if appropriate participants are enrolled. The following eligibility criteria are designed to select participants for whom participation in the study is considered appropriate. All relevant medical and nonmedical conditions should be taken into consideration when deciding whether a particular participant is suitable for this protocol.

Prospective approval of protocol deviations to recruitment and enrollment criteria, also known as protocol waivers or exemptions, is not permitted.

5.1. Inclusion Criteria

Participants are eligible to be included in the study only if all of the following criteria apply:

Age and Sex:

1. Chinese participants must be 18 to 60 years of age, inclusive, at the time of signing the ICD. Among enroll participants, both female and male participants need to be included.
 - Refer to [Appendix 4](#) for reproductive criteria for male ([Section 10.4.1](#)) and female ([Section 10.4.2](#)) participants.

Type of Participant and Disease Characteristics:

2. Male and female participants who are overtly healthy as determined by medical evaluation including medical history, physical examination, laboratory tests, vital signs and standard 12-lead ECGs.
3. Participants who are willing and able to comply with all scheduled visits, treatment plan, laboratory tests, lifestyle considerations, and other study procedures.

Weight:

4. BMI of 17.5 to 28 kg/m², inclusive; and a total body weight >50 kg (110 lb).

Informed Consent:

5. Capable of giving signed informed consent as described in [Appendix 1](#), which includes compliance with the requirements and restrictions listed in the ICD and in this protocol.

5.2. Exclusion Criteria

Participants are excluded from the study if any of the following criteria apply:

Medical Conditions:

1. Positive test result at the investigator's discretion for SARS-CoV-2 infection at the time of Screening or Day -1.
2. Evidence or history of clinically significant hematological, renal, endocrine, pulmonary, gastrointestinal, cardiovascular, hepatic, psychiatric, neurological, or allergic disease (including drug allergies, but excluding untreated, asymptomatic, seasonal allergies at the time of dosing).
3. Clinically relevant abnormalities requiring treatment (eg, acute myocardial infarction, unstable ischemic conditions, evidence of ventricular dysfunction, serious tachy or brady arrhythmias) or indicating serious underlying heart disease (eg, prolonged PR interval, cardiomyopathy, heart failure greater than NYHA 1, underlying structural heart disease, Wolff Parkinson-White syndrome).
4. Any condition possibly affecting drug absorption (eg, gastrectomy, cholecystectomy).
5. History of HIV infection, hepatitis B, or hepatitis C; positive testing for HIV, HbsAg, HbcAb, or HCVAb. Hepatitis B vaccination is allowed.
6. History of sensitivity reactions to ritonavir, or any of the formulation components of PF-07321332 and ritonavir.
7. Pregnant or breastfeeding women.
8. Other medical or psychiatric condition including recent (within the past year) or active suicidal ideation/behavior or laboratory abnormality or other conditions or situations related to COVID-19 pandemic (eg. Contact with positive case, residence, or travel to an area with high incidence) that may increase the risk of study participation or, in the investigator's judgment, make the participant inappropriate for the study.

Prior/Concomitant Therapy:

9. Use of prescription or nonprescription drugs and dietary and herbal supplements within 7 days or 5 half-lives (whichever is longer) prior to the first dose of study intervention (Refer to [Section 6.8](#) Concomitant Therapy for additional details).
10. Current use of any prohibited concomitant medication(s) or those unwilling/unable to use a permitted concomitant medication(s). Refer to [Section 6.8](#) Concomitant Therapy.

11. Participant who have received a COVID-19 vaccine recently which may impact the study evaluation, by the investigator's discretion based on symptoms or impact on safety lab testing.

Prior/Concurrent Clinical Study Experience:

12. Previous administration with an investigational drug within 30 days (or as determined by the local requirement) or 5 half-lives preceding the first dose of study intervention used in this study (whichever is longer).

Diagnostic Assessments:

13. A positive urine drug test.
14. Screening supine BP ≥ 140 mm Hg (systolic) or ≥ 90 mm Hg (diastolic), following at least 5 minutes of supine rest. If BP is ≥ 140 mm Hg (systolic) or ≥ 90 mm Hg (diastolic), the BP should be repeated 2 more times and the average of the 3 BP values should be used to determine the participant's eligibility.
15. Baseline standard 12-lead ECG that demonstrates clinically relevant abnormalities that may affect participant safety or interpretation of study results (eg, baseline QTcF interval >450 msec, complete LBBB, signs of an acute or indeterminate-age myocardial infarction, ST-T interval changes suggestive of myocardial ischemia, second- or third-degree AV block, or serious bradyarrhythmias or tachyarrhythmias). If the baseline uncorrected QT interval is >450 msec, this interval should be rate-corrected using the Fridericia method and the resulting QTcF should be used for decision making and reporting. If QTcF exceeds 450 msec, or QRS exceeds 120 msec, the ECG should be repeated 2 more times and the average of the 3 QTcF or QRS values should be used to determine the participant's eligibility. Computer-interpreted ECGs should be overread by a physician experienced in reading ECGs before excluding a participant. The average of triplicate measurement should be used for eligibility determination.
16. Participants with **ANY** of the following abnormalities in clinical laboratory tests at screening, as assessed by the study-specific laboratory and confirmed by a single repeat test, if deemed necessary:
 - AST **or** ALT level $>1.0 \times$ ULN;
 - Total bilirubin level $\geq 1.5 \times$ ULN; participants with a history of Gilbert's syndrome may have direct bilirubin measured and would be eligible for this study provided the direct bilirubin level is \leq ULN;
 - eGFR <90 mL/min/1.73 m² (with 10% variation) based on the CKD-EPI equation.⁵ The following CKD-EPI equation will be used to calculate eGFR

($S_{Cr, std}$ denotes serum creatinine measured with a standardized assay for serum creatinine):

If female and SCr is ≤ 0.7 mg/dL:

$$eGFR \text{ (mL/min/1.73 m}^2\text{)} = 144 \times (S_{Cr, std}/0.7)^{-0.329} \times 0.993^{\text{age}} (\times 1.159, \text{ if Black})$$

If female and SCr is > 0.7 mg/dL:

$$eGFR \text{ (mL/min/1.73 m}^2\text{)} = 144 \times (S_{Cr, std}/0.7)^{-1.209} \times 0.993^{\text{age}} (\times 1.159, \text{ if Black})$$

If male and SCr is ≤ 0.9 mg/dL:

$$eGFR \text{ (mL/min/1.73 m}^2\text{)} = 141 \times (S_{Cr, std}/0.9)^{-0.411} \times 0.993^{\text{age}} (\times 1.159, \text{ if Black})$$

If male and SCr is > 0.9 mg/dL:

$$eGFR \text{ (mL/min/1.73 m}^2\text{)} = 141 \times (S_{Cr, std}/0.9)^{-1.209} \times 0.993^{\text{age}} (\times 1.159, \text{ if Black})$$

Other Exclusions:

17. History of alcohol abuse or binge drinking and/or any other illicit drug use or dependence within 6 months of Screening. Binge drinking is defined as a pattern of 5 (male) and 4 (female) or more alcoholic drinks in about 2 hours. As a general rule, alcohol intake should not exceed 14 units per week (1 unit = 8 ounces (240 mL) beer, 1 ounce (30 mL) of 40% spirit or 3 ounces (90 mL) of wine).
18. Use of tobacco or nicotine containing products in excess of the equivalents of 5 cigarettes per day or 2 chews of tobacco per day.
19. Blood donation (excluding plasma donations) of approximately 1 pint (500 mL) or more within 60 days prior to dosing.
20. History of sensitivity to heparin or heparin-induced thrombocytopenia.
21. Unwilling or unable to comply with the criteria in the [Lifestyle Considerations](#) section of this protocol.
22. Investigator site staff or Pfizer employees directly involved in the conduct of the study, site staff otherwise supervised by the investigator, and their respective family members.

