2.2. Background

In December 2019, COVID-19 was identified as a new, potentially fatal, respiratory infection caused by the novel coronavirus, SARS-CoV-2. The WHO declared COVID-19 a Public Health Emergency of International Concern on 20 January 2020 and further characterized the disease outbreak as a pandemic on 11 March 2020.¹

PF-07321332 is an orally bioavailable 3CL^{pro} inhibitor shown to be effective against SARS-CoV-2 3CL^{pro} ($K_i = 0.00311 \mu\text{M}$) in a biochemical enzymatic assay. Since the 3CL^{pro} from human coronaviruses are structurally similar and share a high degree of conservation at the active site of the enzyme, the ability of PF-07321332 to inhibit the 3CL^{pro} of other coronaviruses (SARS-CoV-1 and HCoV-229E, MERS, HCoV-OC43, HCoV-HKU1, and HCoV-NL63) was also confirmed, indicating a potential for broad spectrum anti-coronavirus activity. The coronavirus 3CL protease is a virally encoded enzyme that is critical to the SARS-CoV-2 replication cycle, analogous to other obligatory virally encoded proteases (eg, HIV Protease, HCV Protease).² PF-07321332 is being developed as an oral treatment in patients with COVID-19 infection.

Ritonavir is a strong CYP3A4 inhibitor being used to inhibit the metabolism of PF-07321332 in order to increase plasma concentrations of PF-07321332 to values that are anticipated to be efficacious. Ritonavir is not expected to have any pharmacological impact on the SARS-CoV-2 virus and its elimination is not expected to be significantly altered by renal impairment. Ritonavir is being used only as a PK boosting agent.

In vitro and in vivo metabolite profiling suggests that the primary clearance mechanism for PF-07321332 is CYP3A4 mediated oxidation. In a reaction phenotyping study using human liver microsomes in the presence of selective CYP inhibitors, CYP3A4 was predicted to be the major contributor ($f_m = 0.99$) to the in vitro oxidative metabolism of PF-07321332. As such, in the FIH Study, C4671001, the CYP3A4 inhibitor ritonavir was used to enhance the exposure of PF-07321332 in order to achieve plasma levels that are anticipated to be efficacious. **CC1**

CCI

Ritonavir is

extensively metabolized, primarily by CYP3A4.³

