2.2.2. Nonclinical Pharmacokinetics and Metabolism

Hepatic CYP3A enzymes were identified as the main pathway for clearance of PF-07321332 in vitro in liver microsomes (mouse, rat, hamster, rabbit, monkey, and human), hepatocytes (rat, monkey, and human), and in vivo in rat and monkey after repeat oral dosing. In a reaction phenotyping study using human liver microsomes in the presence of selective CYP inhibitors, CYP3A4 was predicted to be the major contributor ($f_m = 0.99$) to the in vitro oxidative metabolism of PF-07321332. No significant CYP3A5 contribution is expected to the metabolism of PF-07321332. Urinary excretion of PF-07321332 following single IV or oral doses in rats was approximately 11%, suggesting minor urinary contributions to the overall elimination of PF-07321332.

PF-07321332 will be combine used with ritonavir (a CYP3A4 inhibitor) instead of monotherapy, CCI

Additional information of the nonclinical PK and metabolism of PF-07321332 is available in the current IB.

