6.8. Concomitant Therapy

Use of prescription or nonprescription drugs and dietary and herbal supplements are prohibited within 7 days or 5 half-lives (whichever is longer) prior to the first dose of study intervention. Limited use of nonprescription medications that are not believed to affect participant safety or the overall results of the study may be permitted on a case-by-case basis following approval by the sponsor. Acetaminophen/paracetamol may be used at doses of ≤ 1 g/day.

Hormonal contraceptives that meet the requirements of this study are allowed to be used in participants who are WOCBP (see [Appendix 4](#)).

Females using hormonal contraceptives or taking hormone replacement therapy may be eligible to participate in this study if they are willing to discontinue therapy at least 28 days prior to the first dose of study treatment and remain off hormonal therapy for the duration of the study. Depo-Provera® must be discontinued at least 6 months prior to the first dose of study treatment.

All concomitant treatments taken during the study must be recorded with indication, daily dose, and start and stop dates of administration. All participants will be questioned about concomitant treatment at admission.

Treatments taken within 28 days before the first dose of study intervention will be documented as a prior treatment. Treatments taken after the first dose of study intervention will be documented as concomitant treatments.

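### The entry washout for ordinary drugs and herbal products tracks drug elimination only, so leftover CYP3A4 induction can reach the Day 1 PK; Section 6.8 should name inducers and give them a longer window

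*Protocol*

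**What the plan says.** - **General washout.** Protocol 5.2, criterion 9, excludes "Use of prescription or nonprescription drugs and dietary and herbal supplements within 7 days or 5 half-lives (whichever is longer") before the first dose. Protocol 6.8 repeats the rule: "Use of prescription or nonprescription drugs and dietary and herbal supplements are prohibited within 7 days or 5 half-lives (whichever is longer").
- **Prohibited medicines.** Criterion 10 excludes "Current use of any prohibited concomitant medication(s) or those unwilling/unable to use a permitted concomitant medication(s). Refer to" Section 6.8. That section sets a paracetamol limit and deals with hormonal products, but names no CYP3A4 inducer or inhibitor.
- **Other washouts.** Criterion 12 covers "Previous administration with an investigational drug within 30 days (or as determined by the local requirement) or 5 half-lives". For hormonal contraceptives and hormone replacement, 6.8 requires women to be "willing to discontinue therapy at least 28 days prior to the first dose of study treatment", with 6 months for a depot product.
- **Medication record.** In 6.8, "Treatments taken within 28 days before the first dose of study intervention will be documented as a prior treatment". No consequence is attached to what is recorded.
- **Clearance.** For PF-07321332, Protocol 2.2.2 states that "CYP3A4 was predicted to be the major contributor" to oxidative metabolism in vitro (fraction 0.99). Protocol 2.2 describes ritonavir as "extensively metabolized, primarily by CYP3A4".
- **Use of Day 1 data.** Day 1 Cmax and AUC12 of PF-07321332 are primary endpoints (Protocol 3). R_ac is Day 10 AUCtau divided by Day 1 AUC12 (Protocol 9.3.2, Table 1). SAP 6.1 uses Day 1 and steady-state parameters in the Chinese-Western comparison.

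**The concern.** A rule of 7 days or 5 half-lives is designed to remove the drug. Induction is a raised amount of enzyme, which returns to normal at the enzyme's own turnover rate once the stimulus has gone. A product with no established half-life, as may be the case for a herbal preparation, falls back on the 7-day limb. The rule can therefore be followed exactly and still admit someone whose CYP3A4 activity is raised.

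Residual induction would lower PF-07321332 exposure, and it could also lower ritonavir, the booster. The effect should be largest on Day 1. The two drugs are given together with no ritonavir lead-in (Protocol 6.1.1), whereas the single-dose part of the first-in-human study started ritonavir 12 hours beforehand (Protocol 2.2.4.1). A low Day 1 AUC12 also raises R_ac. With about 12 evaluable participants (Protocol 9.5), a single affected person has visible weight in the summaries.

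**Working it through.** The washout is an eligibility rule with no calculation behind it, so there is no planned figure to reproduce. The documents give no enzyme half-life, size of induction or percentage inhibition. Those inputs are assumptions, shown as ranges.

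**1. Does the rule clear the drug?** Drug left after 5 half-lives = 0.5^5 = 3.1%. Yes. The 7-day limb governs up to a half-life of 7/5 = 1.4 days. Someone who stopped an inducer 8 days earlier is eligible only if its half-life is no more than 8/5 = 1.6 days.

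**2. How much induction remains once the inducer has gone?** Residual = 0.5^(t/h), where h is the assumed enzyme half-life.

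| h (days) | 7 days | 16 days | 28 days |
|---|---|---|---|
| 1 | 0.8% | 0.0% | 0.0% |
| 2 | 8.8% | 0.4% | 0.0% |
| 3 | 19.8% | 2.5% | 0.2% |
| 4 | 29.7% | 6.2% | 0.8% |

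If first dosing falls at 7 days, Day 10 falls at 16 days, so the residual is much smaller by then. Outside this range, h = 6 days gives 44.5%, 15.7% and 3.9%. The clock here starts when the inducing stimulus ends. Counted from the last intake, the residual is higher, because some drug is still present for a time.

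**3. What could that do to one participant's exposure?** Let E = 1 + (fold - 1) × residual, and let I be the fraction of CYP3A4 inhibited. Then

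exposure ratio = [fm(1 - I) + (1 - fm)] / [fm·E(1 - I) + (1 - fm)].

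Take an assumed 5-fold induction with 20% remaining, so E = 1 + 4 × 0.2 = 1.8:
- No inhibition: 1/(0.99 × 1.8 + 0.01) = 0.56 for fm 0.99, and 1/(0.80 × 1.8 + 0.20) = 0.61 for fm 0.80.
- 90% inhibition, fm 0.99: 0.109/0.1882 = 0.58.
- 98% inhibition, fm 0.80: 0.216/0.2288 = 0.94.

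With 1% remaining, E = 1.04 and the ratio is at least 0.96. The blunting by ritonavir is strong only if a material share of clearance bypasses CYP3A4. The 0.99 in the protocol refers to in vitro oxidative metabolism, not total clearance.

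**4. What does one affected participant of 12 do to the summary?** This step takes the exposure ratio f as given; it is not derived from step 2.
- Geometric-mean shift = f^(1/12) - 1. For f = 0.85 it is -1.3%; for f = 0.5 it is -5.6%.
- R_ac, if Day 10 is unaffected, shifts by (1/f)^(1/12) - 1: +1.4% and +5.9%.
- With an assumed 30% geometric CV, the log-variance becomes ln(1.09) + (ln f)²/12. The CV goes to about 30.4% for f = 0.85 and about 37% for f = 0.5.

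**5. How demanding is f = 0.5?** With no inhibition and all clearance induced, the fold needed is 1 + (1/f - 1)/residual. For h = 4, 2 and 1 days this is 1 + 1/0.297 = 4.4, 1 + 1/0.088 = 12 and 1 + 1/0.0078 = 129. For f = 0.85 it is 1.6, 3.0 and 24. Halved exposure therefore needs slow turnover or strong induction.

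**The case against.** Several counter-arguments have weight.

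- **Other washouts exist.** A reader might infer that 7 days or 5 half-lives is the protocol's only drug washout. It is not: there are 30-day, 28-day and 6-month rules. They cover only investigational and hormonal products, so the gap for ordinary inducers remains.
- **The event is unlikely.** Participants must be overtly healthy (criterion 2 of Protocol 5.1), and clinically significant disease is excluded. This stands, and it is why the point is a precaution.
- **Ritonavir suppresses the pathway.** Protocol 4.3 describes CYP3A4 inhibition as near maximal. This would blunt the effect, particularly at steady state. It does not dispose of Day 1, and ritonavir is itself a CYP3A4 substrate.
- **Discretion exists.** Protocol 5 asks that all relevant conditions be weighed. SAP 5.3.2 drops a known biased parameter estimate from the summaries, with vomiting as its example. Medians, listings and individual box-plot points (SAP 6.1) would show a low value. These are routes, but none mentions prior inducer use. Leaving someone out of the summary after the fact is weaker than an entry rule.
- **The shift is small against sampling error.** With an assumed 30% CV and n = 12, the 95% interval for a geometric mean is exp(±2.201 × 0.2936/√12), or 0.830 to 1.205. Shifts of -1.3% and -5.6% lie well inside it. A reader might infer that carry-over would pass for an ethnic difference. The documents do not support that: no hypothesis is tested, no decision rule is set (SAP 5.1), and the comparison also uses steady-state data.

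**Conclusion.** The gap is real and worth closing. For ordinary prescription, nonprescription and herbal products, the protocol sets a washout that does not necessarily allow CYP3A4 induction to wear off. Criterion 10 points to a section that names no inducer, and the 28-day record triggers no action. The direction is clear: lower exposure, mainly on Day 1, and a higher R_ac.

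The size rests on assumptions outside the documents. With an enzyme half-life of 1 to 4 days, 0.8% to 29.7% of induction remains at 7 days and under 1% at 28 days after the inducer has gone. Separately, one affected participant in 12 moves the geometric mean by about -1.3% to -5.6% for exposure ratios of 0.85 to 0.5. The two ranges are not a single chain and should not be multiplied together.

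Two stronger conclusions are tempting and unsupported. One is that the rule always leaves induction behind; with fast turnover almost nothing remains. The other is that the study's PK will be biased; the documents show only that an affected participant could be admitted. This is an avoidable, low-probability risk.

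**What to change.** In criterion 9 and Section 6.8, exclude use of moderate or strong CYP3A4 inducers, including herbal products known to induce CYP3A4, within 28 days or 5 half-lives (whichever is longer) before the first dose. The half-life limb must stay: a flat 28 days would shorten the present washout for any inducer with a half-life above 28/5 = 5.6 days. List the inducers, herbal ones included, in Section 6.8 as the prohibited medicines to which criterion 10 refers. Keep 7 days or 5 half-lives for all other products.

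The 28 days matches the period for which Section 6.8 already records prior treatments, so no new procedure is needed for that window. The cost is a short list, a sentence or two of eligibility text and a few extra screen failures.
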